7.1 Initial Retrospective Evaluation

Once the subject has been screened and confirmed that they meet all inclusion and exclusion criteria, the subject will be consented. A medical record review will commence to obtain baseline information. The subject will be scheduled for the next annual follow-up that they are due for based on the original surgery date and as per the Evaluation Schedule on page 4. The earliest visit accepted will be five years postoperative, which means subjects will have to have a surgery date of 2015 or earlier. The initial medical record review will include obtaining: demographic/medical history, surgical details, a baseline evaluation at either two weeks, six weeks or three months and Knee Society Score elements; pain level and range of motion values. The anteroposterior (AP, standard and long-standing), mediolateral and merchant/skyline x-rays are optional. The AP long-standing film will only be used as a reference to determine if the subject meets the protocol inclusion of not having a preoperative varus or valgus deformity of greater than 15 degrees.

For the initial retrospective cases, as much of the preoperative data and baseline data will be retrospectively collected from the medical records upon completion of written consent. The patient reported outcomes (SF-12, LEAS, Activity Questionnaire and KOOS) will not be available prior to consent but will be collected from the point of consent forward to ten years.

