8.1 Adverse Event (AE) Reporting Requirements for this study

- All adverse events that meet the definition of serious (not to include elective surgeries)
- All AE's related to operative site, regardless of seriousness

See Adverse Event Decision Tree - Figure 1

Adverse Event Reporting Period

The study period during which adverse events must be reported is normally defined as the period from the initiation of any study procedures to the end of the study treatment follow-up. In other words, the start of study procedures is considered to be the point of consent. Therefore, any adverse events which fit the protocol defined reportable events must be reported from the time of obtaining consent throughout the study duration.

At each contact with the subject, the investigator must seek information on adverse events by specific questioning and, as appropriate, by examination. Information on protocol defined adverse events should be recorded immediately in the source document, and also in the appropriate adverse event module of the case report form (CRF). All clearly related signs, symptoms, and abnormal diagnostic procedure results should be recorded in the source document, though they should be grouped under one diagnosis. The clinical course of each event should be followed until resolution or until it is determined at the end of the study that the adverse event will not resolve.

During the medical record review of the retrospectively enrolled cases, any operative site adverse events will be documented as per the usual procedure. For prospective follow-up, these cases will adhere to the adverse event reporting described above.

General Physical Examination Findings

At screening for inclusion into the study, any clinically significant abnormality should be recorded as a preexisting condition. During the study, any new clinically significant findings/abnormalities that meet the definition of a protocol defined adverse event must also be recorded and documented as an adverse event.

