9.2.2 Safety Analysis

All adverse events will be listed, tabulated, and summarized by event, number, and percent of cases/patients. Adverse event rates and exact 95% confidence intervals will be presented.

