10.1 Subject Recruitment and Screening

Patients will be recruited at the study sites by a review of medical records for prior cases receiving the Triathlon PKR unicompartmental device. Once a patient is identified as having a PKR unicompartmental device implanted outside of the initial prospective study, it will be determined if they are deceased or had the device revised, which would exclude them during the screening process. Once a patient is identified as a potential study candidate, the study coordinator will review all the inclusion and exclusion criteria to ensure the patient meets those criteria. If that screening is successful, the study coordinator will contact the patient to conduct a telephone screening to review the study details and inquire as to the level of interest to participate. If there is interest, it will be determined if the patient has the capacity to give informed consent, and if so, a verbal informed consent will be provided. A signature will be obtained on the formal approved informed consent document to complete the enrollment into study.

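### Section 8.1 gives retrospective knees two unreconciled rules, so a post-implant knee problem already present at screening can be filed as preexisting and left out of the adverse event rates

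*Combined protocol and SAP*

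**What the plan says.** Protocol Section 8.1 contains four provisions that bear on a retrospective knee.

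- The reporting window: protocol-defined events "must be reported from the time of obtaining consent throughout the study duration".
- A provision for the retrospective cohort alone: "During the medical record review of the retrospectively enrolled cases, any operative site adverse events will be documented as per the usual procedure".
- A general provision, under the subheading on physical examination findings: "At screening for inclusion into the study, any clinically significant abnormality should be recorded as a preexisting condition".
- Its companion: "During the study, any new clinically significant findings/abnormalities that meet the definition of a protocol defined adverse event must also be recorded".

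The last two name no cohort.

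On timing, Section 7.1 requires a surgery date in 2015 or earlier for retrospective cases and says "The earliest visit accepted will be five years postoperative". On the means of screening, Section 10.1 says "Patients will be recruited at the study sites by a review of medical records for prior cases receiving the Triathlon PKR unicompartmental device", and that "the study coordinator will contact the patient to conduct a telephone screening". It describes no screening examination.

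On use of the data, Section 9.2.2 says "All adverse events will be listed, tabulated, and summarized by event, number, and percent of cases/patients", with exact 95% confidence intervals and no stated split by cohort. Sections 2.2 and 12.3 compare the rates with published literature, at 10 years in Section 12.3.

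**The concern.** For a patient screened before surgery, treating whatever is found at screening as preexisting is sound: it keeps the arthritis that led to the operation out of the event count. A retrospective patient has already carried the implant for years when screened, and version 2.0 did not adapt the rule. Taken literally, it labels knee pain, stiffness or radiographic change that began after the operation as preexisting. Because such a problem is not *new* after consent, it need not be reported later either.

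The cohort-specific sentence in the same section points the other way for events in the medical record. The plan states no order of precedence, so two sites could classify the same knee differently.

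At stake are the rates of persistent, unrevised knee problems. Excessive knee pain, component loosening and progression of arthritis are rows of the literature table in Section 12.3. Any misfiling runs in one direction: it lowers the reported rate, and only through the retrospective cohort.

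**Working it through.** **Step 1. What each rule reaches.** The provisions are set side by side for a retrospective knee whose problem began after implantation.

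| Operative-site problem | Record-review sentence | Screening rule | Outcome |
|---|---|---|---|
| Charted as an event, resolved before screening | Adverse event | Not engaged | Counted |
| Charted as an event, still present at screening | Adverse event | Preexisting | Rules conflict; the cohort-specific one is the natural choice |
| Charted only as a symptom, still present | Unclear | Preexisting | May be lost |
| Not charted, reported during screening | Does not reach it | Preexisting | Likely lost |
| Not charted, found at the first study visit, earlier onset | Does not reach it | Counts only if new | Unclear |
| Onset after consent | Not needed | New finding | Counted |

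The exposure lies in rows three to five, and in row two if a site follows the general rule.

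**Step 2. Whether other text settles it.**

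- Section 8.2 defines an adverse event by a change in the subject's medical baseline. Section 7.1 takes baseline for these cases from preoperative data and one early postoperative evaluation. This favours counting later-onset problems, but Section 8.1 does not make the link.
- Section 7.1 lists what the record review is to obtain (history, surgical details, a baseline evaluation, Knee Society Score elements). Adverse events are not in that list.
- The postoperative evaluation form in Appendix E asks about events since the last visit. At a retrospective case's first study visit, at 5, 7 or 10 years, a long-standing problem does not clearly fit that question.
- The adverse event form in Appendix E already takes an event date and a Pre-Op, Intra-Op or Post-Op classification. It can hold the right answer, but it comes into play only once someone has decided that the finding is an adverse event.

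**Step 3. Size.** The plan gives no misfiling rate, so there is no figure of its own to reproduce. The inputs are:

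- Cohort sizes from Section 3.3: 80 prospective and at least 95 retrospective, total 80 + 95 = 175.
- r: the true percentage of knees with a given event, assumed equal in both cohorts.
- f: the share of retrospective knees with the event in which it is filed as preexisting (assumed).

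Reported pooled rate = [80r + 95r(1 − f)] / 175 = r(1 − 95f/175) = r(1 − 0.543f).

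| f (assumed) | Relative fall | Reported rate if r = 10% |
|---|---|---|
| 10% | 5.4% | 9.5% |
| 25% | 13.6% | 8.6% |
| 50% | 27.1% | 7.3% |
| 100% | 54.3% | 4.6% |

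The last row is an arithmetical ceiling and not a realistic case. It would need every event in the 95 knees to be still present at screening and every one to be misfiled despite the record-review sentence.

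**The case against.** The strongest reply is that Section 8.1 already deals with this cohort. The record-review sentence is specific, the screening rule is general, and a specific provision is ordinarily read as controlling. **This stands for operative-site events that the chart identifies as events.**

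Second, the screening rule sits under a heading on physical examination, whereas retrospective screening is a chart check and a telephone call. This narrows the opportunity for misfiling. It does not remove it, because the sentence covers any clinically significant abnormality at screening, and the first study examination then counts only what is new.

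Third, Section 8.1 obliges the investigator to ask about adverse events at each contact, and the event form records onset relative to surgery. Both help, but neither says how to classify a problem that began after surgery and before consent.

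Fourth, the adverse event decision tree (Figure 1) and the separate guide to the case report forms are not in the text available here and might settle the order of precedence. That cannot be excluded.

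Fifth, the safety analysis is descriptive, with no test or threshold. The Knee Society function analysis and the survivorship analysis do not depend on this rule. That is correct and limits the consequence.

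A reader might infer that the screening rule removes post-implant knee problems from the rates wholesale, or that pooled rates could be roughly halved. The documents do not support either reading. Charted events are covered. Several rows of the literature table, such as intraoperative fracture and superficial wound infection, need not still be present years later. Knees already revised are excluded at screening under Section 10.1, so they never reach this rule; that exclusion is a separate matter.

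**Conclusion.** The point holds as an unreconciled overlap of two rules with a residual gap. The gap consists mainly of operative-site problems that began after implantation, are present at screening, and are either absent from the chart or noted there only as symptoms. For these, Section 8.1 allows classification as preexisting and therefore omission from the pooled rates. The direction is known (downward, through the retrospective cohort only) and the amount is not.

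The relative fall of 0.543f assumes equal true risk in the two cohorts and the planned 80 and 95 knees. No value of f is supported by the documents. It should be small if sites apply the record-review sentence to charted events, because f is then limited largely to problems the chart does not show or does not label. The matter deserves correction because the rates are compared with literature and the remedy is cheap, not because a large bias has been shown.

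**What to change.** Add to Section 8.1, and mirror in the guide to the case report forms:

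- For retrospective cases, a preexisting condition is one with onset before the index surgery.
- Any operative-site abnormality with onset after the index surgery, whether found in the records, at screening or at the first study visit, is recorded as an adverse event with its onset date.

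The existing adverse event form already has fields for the event date and its timing relative to surgery, so no new data field is needed. The change concerns recording only and leaves patient care untouched. Its cost is the text itself, some additional adverse event forms for the retrospective cases, and a slightly higher reported adverse event rate.

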8.2 General Adverse Event Definitions

Following is a list of definitions related to adverse events.

Adverse Event

An *adverse event* (AE) is any untoward medical occurrence in a clinical investigation subject, which changes the medical baseline of the subject. An adverse event can be an unfavorable and unintended sign, symptom or disease, whether or not related to the study device (AEs may also

CONFIDENTIAL

be referred to as complications). In this study only adverse events that are either serious or related to the operative site are to be reported (see Figure 1).

Anticipated Adverse Event

An *anticipated adverse event* is an AE, of which the nature, severity or degree of incidence is known and identified in applicable product labeling, published literature or study protocol. The list of events which are anticipated are provided in the Risk/Benefit Assessment (section #12).

Adverse Device Effect

An *adverse device effect* (ADE) is a negative change in the subject's health that may have been caused by or associated with the use of the device.

Serious Adverse Event

A serious adverse event (SAE) meets one or more of the following definitions:

- Resulted in in-patient hospitalization
- Resulted in prolonged existing hospitalization
- Resulted in persistent or significant disability/incapacity
- Resulted in permanent impairment of a body function or permanent damage to a body structure
- Necessitated medical or surgical intervention to preclude permanent impairment of a body function or permanent damage to a body structure
- Was a life-threatening situation
- Resulted in patient death

Unanticipated Adverse Device Effect

An *unanticipated adverse device effect* (UADE) is any serious adverse effect on health, safety or any life-threatening problem or death caused by, or associated with a device, if that effect, a problem or death not previously identified in nature, severity or degree of incidence, or any other unanticipated serious problem associated with a device and related to the rights, safety or welfare of subjects.

8.3 Study Sponsor Notification by Investigator

The sponsor requests that certain events be faxed to us for timely notification. Those that need to be submitted to the sponsor are:

Events which are serious as per the definition of SAE.

Events which are deemed to be "related to" or "uncertain" in regard to relation to the

device.

A copy of the completed Adverse Event (AE) form must be completed by the investigator and sent to the study sponsor within 24 hours. The investigator will keep a copy of this AE form on file at the study site and submit the hard copy as per case report form data submission procedures.

Report noted events to:

[name] [contact]

[contact]

At the time of the initial report, the following information should be provided:

Subject Number

A description of the event

Date of onset

Current Status

Whether the study treatment was discontinued

The Investigator's assessment of the association between the event and study

treatment

8.3.1 EC/IRB Notification by Investigator

Reports of adverse events (including follow-up information) must be submitted to the IRB according to their specific requirements. Copies of each report and documentation of IRB notification and receipt will be kept in the Clinical Investigator's binder.

8.4 Medical Monitoring

It is the responsibility of the Investigator to oversee the safety of the study at his/her site. This safety monitoring will include careful assessment and appropriate reporting of adverse events as noted above. The Sponsor will conduct formal investigations via the Product Surveillance

Department of those adverse events which are submitted through our Produce Experience Report System.

9 Statistical Plan

9.1 Efficacy

9.1.1 Primary Efficacy Parameters

The primary efficacy parameter is the mean 10-year KSS Function Score combining the prospective and retrospective cases.

9.1.2 Secondary Efficacy Parameters

The secondary efficacy parameter is revision or removal of any component.

9.1.3 Primary Efficacy Hypothesis

The null hypothesis: H_0 , the mean 10-year KSS function (u) is inferior to 84 points with a margin of 6 points. The alternative hypothesis to be tested is, H_a , the mean 10- year KSS function is non-inferior to 84 points with a margin of 6 points.

 H_0 : u-84 < -6 H_a : $u-84 \ge -6$

9.1.4 Primary Efficacy Analysis

A 90% 2-sided confidence interval of the mean 10-year KSS function will be computed. If the lower bound of the confidence interval is greater than 78 then the non-inferiority hypothesis will be supported. If the lower bound of the confidence interval is above 84, then the superiority will be supported

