Appendix A Component Listing

Appendix B FDA 510K Clearance Letters

Appendix C Product Labeling

Appendix D Model Informed Consent Form

Appendix E Sample Case Report Forms

Appendix F Patient Retention Program

List of Abbreviations

AE Adverse Event
AP Anteroposterior
AVN Avascular Necrosis
BMI Body Mass Index

CAD Computer Assisted Design
CSM Clinical Study Manager
DCF Data Clarification Form
EDC Electronic Data Capture
FEA Finite Element Analysis
GCP Good Clinical Practice

HIPAA Health Insurance Portability and Accountability Act

KSS Knee Society Score

KOOS Knee and Osteoarthritis Outcome Score

M/L Medio/Lateral
ML Mediolateral
OA Osteoarthritis

PCL Posterior Cruciate Ligament PER Product Experience Report

PI Primary Investigator
QOL Quality of Life
ROM Range of Motion
SC Study Coordinator
SF-12 Short-Form 12
TA Traumatic Arthritis

UHMWPE Ultra High Molecular Weight Polyethylene UKA Unicompartmental Knee Arthroplasty

Study Synopsis

Title	The Triathlon [®] PKR Unicondylar Knee System Outcomes Study
Short Title	Triathlon [®] PKR Study
Protocol Number	66
Phase	Post-marketing
Methodology	This study is a prospective, post-market, multi-center evaluation of the Triathlon [®] PKR unicondylar knee system with an additional retrospective enrolled and prospectively followed cohort of cases.
Study Duration	10-year follow-up for each case
Study Center(s)	A minimum of four centers will participate.
Objectives	Primary: The 10-year mean KSS Function Score is comparable to the Triathlon CR KSS Function Score at 10-years. Secondary: A 10-year Kaplan Meier survival analysis will be presented including only prospective cases.
Additional Data Collection	To compare OR time, hospital stay, blood loss, return to ROM, KSS, activity level, adverse event rates, and radiographic data to UKA.
Reference Therapy	Triathlon CR Stryker Sponsored Study; Clinical Trials NCT 00966979; Survivorship data from national registries will supplement the study survivorship data.
Number of Subjects	A total of 175 cases (knees) will be enrolled. There are 80 cases enrolled from the prospective cohort and a planned minimum 95 cases is the goal from the retrospective cohort.

Inclusion Criteria

- 1) The subject is a male or non-pregnant female 21-75 years of age at the time of enrollment.
- 2) The subject requires a primary cemented unicompartmental knee replacement.
- 3) The subject has a diagnosis of osteoarthritis (OA) or post-traumatic arthritis (TA).

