2.1 Efficacy

2.1.1 Primary

The 10-year mean KSS Function Score is comparable to 84 points (the mean of the Triathlon CR KSS Function Score at 10-years postoperatively). The mean PKR 10-year score is calculated from both the prospective and retrospective cases.

CONFIDENTIAL

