4.2 Exclusion Criteria

- 1) The subject has inflammatory arthritis or avascular necrosis (AVN).
- 2) The subject is obese, BMI >35.
- 3) The subject has a history of total or unicompartmental (contralateral compartment and/or patellofemoral joint) reconstruction of the affected joint.
- 4) The subject has a history of ACL reconstruction.
- 5) The subject has had a high distal femoral, or proximal tibial osteotomy.
- 6) The subject has a mental, neuromuscular or neurosensory disorder, which would create an unacceptable risk of prosthesis instability, prosthesis fixation failure, or complications in post-operative care and/or limit the ability to assess the performance of the device.

- 7) The subject has a systemic or metabolic disorder leading to progressive bone deterioration that the surgeon feels would affect the overall outcome of the study.
- 8) The subject is immunologically suppressed or is receiving chronic steroids (>30 days duration).
- 9) The subject has a known sensitivity to device materials.
- 10) The subject's bone stock is compromised by disease and/or infection which cannot provide adequate support and/or fixation to the prosthesis.
- 11) The subject's bone stock is compromised by a prior implantation which cannot provide adequate support and/or fixation to the prosthesis.
- 12) The subject has an active or suspected latent infection in or about the knee joint.
- 13) The subject is a prisoner.

5 Subject Enrollment

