9.4 Statistical Methodology

9.4.1 Data Summary

Descriptive statistics will be computed for all baseline conditions and demographic parameters. If appropriate, the data will be presented by appropriate subgroups (e.g., center). In general, follow-up data will be summarized according to visit. For parameters

represented by continuous variables (e.g., blood loss, KSS), the summaries will consist of the mean, median, standard deviation, minimum, and maximum values. For categorical variables (e.g., revision), the number and percent in each category will be presented. Ninety percent confidence intervals will be presented where tests of non-inferiority will be performed, otherwise the 95% confidence interval will be presented. Descriptive statistics and statistical comparisons for important demographic, efficacy, and safety variables will be provided in tables.

Statistical analyses utilizing SAS® software version 9.1 or higher will be used.

Sample Size Justification

The Stryker sponsored Triathlon CR study has a mean 10-year KSS function 84 points and a standard deviation of 21, A literature review shows the minimal clinically important difference for KSS function is 6 points⁶⁰, with a 5% type I error rate and a power of 80%, the sample size is 76. By factoring in a 20% attrition rate at 10 years postoperatively, the adjusted sample size will be 95 cases.

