	Appendix E	
	Sample Case Report Forms	

Stryker® Triathlon PKR Outcomes Study INCLUSION / EXCLUSION [name] Triathlon PKR Outcomes Study INCLUSION / EXCLUSION					Page 1 of 1			
CENE	Study # Site # Subject # GENERAL INFORMATION							
PATII	ENTIN	IITIAL				OPERATIVE SIDE: (use one form per side)	Right	Check One)
I. INC	LUSIO		TERIA				DATE INFORME	D CONSENT SIGNED
1.	Yes	O	years of age a	t the time of e		21-75	M M	M / Y Y Y Y
2.	0					ompartmental knee re		
3.	0	_		-	· ·	OA), or post-traumatic		
4. 5.	00	_		-		ollateral ligaments and contracture and grea	-	entous instability is present. O degrees of flexion.
6.	0	0	The subject's	preoperative r	mechanical alignme	ent is less than 10 de	grees of va	arus and 10 degrees of valgus.
7.	0	01	The subject ha	s signed the	IRB approved stud	y specific Informed Pa	atient Cons	ent Form.
8.	0	0	The subject is	willing and al	ole to comply with	postoperative schedul	led clinical	and radiographic evaluations
			and rehabilitat		h	-11 for the metters 4	- h	Had in the aturds
II. EX	CLUSI		TAIL OF THE S	above must	be answered "Ye	es" for the patient t	o be enro	nied in the study.
	Yes	No						
1.	0	0	The subject h	as inflammato	ory arthritis or avas	cular necrosis (AVN).		
2.	0	0	The subject is	obese, BMI	> 35.			
3.	0	0	The subject h	-	·	artmental (contralatera	al compartn	ment and/or patellofemoral joint)
4.	0	0	The subject h	as a history o	of ACL reconstruction	on.		
5.	O	0	The subject h	as had a high	n distal femoral, or	proximal tibial osteoto	omy.	
6.	0	0	risk of prostl	nesis instabilit		on failure, or complica		ould create an unacceptable st-operative care and/or
7.	0	0			c or metabolic diso all outcome of the		essive bone	e deterioration that the surgeon
8.	0	0	The subject i	s immunologi	cally suppressed, o	or is receiving chronic	steroids (>30 days duration).
9.	0	0			ensitivity to device			
10.	0	0			s compromised by he prosthesis.	disease and/or infecti	ion which o	cannot provide adequate
11.	0	0	and/or fixatio	n to the prostl	nesis.			ot provide adequate support
12.	0	0	The subject h	as an active	or suspected latent	infection in or about t	he knee jo	int.
13.	0	0	The subject is					
						o" for the patient to		
III. CC	MMEN	2TI	Please fax to	Stryker at [name] attn	: Study Manager for	a patient II	D to be assigned.
ni. 00			19113					
- 0								
INVE	STIGA	IOR	IAME (PRINT):			For Stryker U	-04	INITIAL/DATE:
INVE	STIGA	FOR S	IGNATURE:			Stamp Date Re	ceived:	Receipt

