○>0-< 1.5 cm	I. OUTERBRIDGE CLASSIFICATION: CONTRALATERAL PATELLO FEMORAL
○1.5 - 3 cm	COMPARTMENT: (Check one) JOINT: (Check one)
○ > 3 cm	○ Grade 0
	○ Grade I
Sub Vastus	Grade II

Stryker®		Outcomes Study IAL EVALUATION - KSS	Page 1 of 2
[name]		PATIENT ID: 6	6 Site # Subject #
GENERALINFORMATION	HE ELECTRONIC CHARLES		
PATIENT INITIALS: (If there is no middle initial please use "-")		VISIT DATE:	M M M Y Y Y Y
OPERATIVE SIDE:	O Left (Check one) VISIT: O 2 Week	6 3 1 2 Week Month Year Year	5 7 10 Unscheduled Year Year Year (Specify reason in
LWEIGHT	vveek	Week Month Year Year	rear rear rear Comments)
A. WEIGHT:	lbs.		almand statement
II. KSS			
B. PATIENT CATEGORY: (Chec	k one)		
	osite knee successfully replaced)		
O Unilateral, Other Knee Symp			
Multiple Arthritis or Medical			
III. KSS - PAIN/MOTION SCORE			(BS) 11 (1 2 2 1 0 2 0 1 2 1 1 1 1 1 1 1 1 1 1 1
C. PAIN: (Check one)		D. RANGE OF MOTION: F	ctension Flexion
None	Moderate Occasional		TICKION TICKION
Mild or Occasional	Moderate Continual	Active:	
Mild or Occasional, Stairs O	~	Passive:	
Mild or Occasional, Walking			
E. STABILITY: (Amount of Motio	n)	F. ALIGNMENT - TIBIO-FEMO	RALANGLE: (Check one)
Anteroposterior (Check one)	Mediolateral (Check one)	O Valgus	
O < 5 mm	O < 5°		
5 - 10 mm	O 5° - 9°	O Varus	
O > 10 mm	O 10° - 14°		
	O > 14°		
IV. KSS - FUNCTION SCORE			
G. WALKING: (Check one)	H. STAIRS: (Check of		ALKING AIDS: (Check one)
Unlimited	Normal Up & Do	·	None
O > 10 Blocks	Normal Up; Dow	n with Rail (Cane
5 - 10 Blocks	Up & Down with	Rail (Two Canes / One Crutch
O < 5 Blocks	Up with Rail; Un	able Down (Crutches or Walker; Cannot Walk / Wheelchair
Housebound	Unable		Camot Walk / Wheelchair
O Unable			
V. OTHER			2.是19年1日从2017年6日本
J. TRANSFER ACTIVITY - CHAIN TO STANDING: (Check one)	K. CREPITUS: (Check	cone) L. ANTERIOR K	NEE PAIN: (Check one)
		Present Absent	
Without Upper Extremity Su		O Present	
With Upper Extremity Support	ırt	If present a	at 1 yr or later, please explain
Cannot Transfer			

Stryker® Triathlon PKR Outcomes Study POST-OP FUNCTIONAL EVALUATION - KSS								
[name]	•		F	PATIENT ID:	6 6 Study #			Subject #
GENERAL INFORMATION		21 5 "SU	77 57		West N			
PATIENT INITIALS: (If there is no middle initial please use *-*)								
OPERATIVE SIDE: Right	Check one)	VISIT : O 2 Week	6 Week M	3 1 Month Year	O 2 Year	O O 5 7 Year Year	10 Year	Unscheduled (Specify reason in Comments)

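### The primary analysis averages a person-level KSS Function score over knees with no patient-level variance stated, so a simple 90% CI is too narrow if any patient has two study knees

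*Combined protocol and SAP*

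**What the plan says.** - **Unit.** The Study Synopsis and section 3.3 count knees: "A total of 175 cases (knees) will be enrolled". Section 2.1.1 takes the primary mean over cases: "The mean PKR 10-year score is calculated from both the prospective and retrospective cases". Section 9.1.1 defines the primary parameter in the same way.
- **Interval.** Section 9.1.4: "A 90% 2-sided confidence interval of the mean 10-year KSS function will be computed". Non-inferiority needs a lower bound above 78, and superiority needs one above 84. No variance estimator is named.
- **Score.** The section of the case report form headed "KSS - FUNCTION SCORE" (Appendix E) holds three items: walking distance, stairs and walking aids. None refers to a side.
- **Eligibility.** Exclusion 3 in section 4.2 covers only prior "reconstruction of the affected joint". No other criterion excludes a patient whose opposite knee is also a study knee.
- **Forms.** Several forms in Appendix E, including the eligibility form, carry the instruction "use one form per side".
- **Sample size.** Section 9.4.1 starts from an SD of 21 and a margin of 6 points: "with a 5% type I error rate and a power of 80%, the sample size is 76". This becomes 95 after 20% attrition.
- **Safety.** Section 9.2.2 does separate the two units: "All adverse events will be listed, tabulated, and summarized by event, number, and percent of cases/patients". The efficacy sections do not.

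**The concern.** Two study knees in one patient, scored at the same time, would receive the same KSS Function score, because the items are about the person. Entering that score twice as if it were two independent observations overstates the information in the sample, and the standard error comes out too small. The lower confidence bound is then too high.

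Both claims in section 9.1.4 rest on that lower bound, so the error favours the device each time: the chance of wrongly declaring non-inferiority or superiority exceeds the 5% implied by a 90% two-sided interval. What is at stake is the error rate. Power is not the difficulty, because 175 planned knees are well above the number the calculation requires.

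**Working it through.** **1. The plan's own figure.** Inputs from section 9.4.1: SD 21, margin 6, 5% type I error, 80% power, 20% attrition. One-sample formula, one-sided 5% (equivalent to the 90% two-sided CI):

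n = ((1.645 + 0.842) × 21 / 6)² = 75.7, rounded up to 76; 76 / 0.8 = 95.

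Both figures reproduce exactly. The formula treats every observation as independent, with no allowance for two knees in one patient.

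**2. Variance with bilateral patients.** Let p be the share of patients with two study knees (at most two each) and ρ the within-patient correlation. The share of knees that come from bilateral patients is f = 2p/(1+p). The variance of the mean over N knees is (SD²/N) × DE, with DE = 1 + fρ. Then:

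- true one-sided error of the simple CI = 1 − Φ(1.645/√DE)
- required widening = √DE − 1
- power with the correct variance = Φ(6/(21 × √(DE/140)) − 1.645), at a true mean of 84 and 140 evaluable knees (175 × 0.8)

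Neither p nor ρ is in the documents, so both are assumptions. ρ = 1 represents two knees scored at the same visit. ρ = 0.5 allows for staged operations, since follow-up is timed from the surgery date (section 7.1) and the two 10-year scores may be taken at different times.

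| p | f | ρ | DE | One-sided error | CI should be wider by | Power at 140 knees |
|---|---|---|---|---|---|---|
| 0% | 0 | any | 1.000 | 5.0% | 0% | 95.9% |
| 5% | 0.095 | 0.5 | 1.048 | 5.4% | 2.4% | 95.1% |
| 5% | 0.095 | 1 | 1.095 | 5.8% | 4.7% | 94.4% |
| 15% | 0.261 | 0.5 | 1.130 | 6.1% | 6.3% | 93.8% |
| 15% | 0.261 | 1 | 1.261 | 7.1% | 12.3% | 91.4% |
| 30% | 0.462 | 0.5 | 1.231 | 6.9% | 10.9% | 92.0% |
| 30% | 0.462 | 1 | 1.462 | 8.7% | 20.9% | 87.5% |

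**3. Where the range of p comes from.** Section 12.3 reports 1,599 cases in 1,392 patients in the sponsor's total-knee studies: (1,599 − 1,392)/1,392 = 207/1,392 = 14.9%, if nobody had more than two knees. The unicompartmental series in Table I vary widely: 56 knees/56 patients is 0%; 161/158 is 3/158 = 1.9%; 516/427 is 89/427 = 20.8%; 181/117 is 64/117 = 54.7%. At p = 55% and ρ = 1, DE = 1.710, the error is 10.4% and power is 82.7%. Power falls below 80% only if DE exceeds 140/75.7 = 1.85.

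**4. In points.** At 140 knees the simple half-width is 1.645 × 21/√140 = 2.92. At p = 15% it should be 3.10 (ρ = 0.5) to 3.28 (ρ = 1), and at p = 30%, ρ = 1 it should be 3.53. The observed mean needed for non-inferiority therefore moves from 80.92 to at most 81.53 in the scenarios tabulated.

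**5. Simulation.** With 140 knees, true mean 78, ρ = 1 and 20,000 runs, the simple CI wrongly declares non-inferiority in 5.8% / 7.2% / 8.8% of runs at p = 5% / 15% / 30%. A cluster-robust CI does so in 5.0% / 5.2% / 5.0%.

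**The case against.** **The unit is not stated consistently.** Section 9.4.3 defines the analysis population in terms of subjects, and section 3.3 uses subjects and cases for the same count. Read literally, that could mean one knee per patient. But the synopsis and section 3.3 equate cases with knees, the primary mean is over cases, and no one-knee rule appears anywhere. The mixed wording is a reason to settle the point; it does not settle it.

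**No document says that any patient has two study knees.** This is true, and it stands as a limit. The KSS form's patient categories foresee bilateral replacement, but not necessarily with two study devices.

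**The illustrated shares may be high.** The 15% proxy comes from a different procedure, and some series in Table I have very few bilateral patients. At 1.9% the error is only 5.3% (ρ = 1) or 5.2% (ρ = 0.5). If the 80 prospective knees all came from different patients and 15% applied only to the 95 retrospective knees, it would be 6.2% or 5.6%. The value 0.5 for ρ also has no source in the documents. These points bear on the size, not the direction: any positive correlation makes the simple CI too narrow.

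**The practical effect is small.** The conclusion changes only if the observed mean falls within a band of about 0.6 point or less near 81, or the corresponding band for superiority. That is fair, and it is why the point is moderate in weight.

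**Other remedies exist.** One prespecified knee per patient, or a patient-level mean, would also remove the double counting. Both change which mean is estimated; a clustered variance keeps the case-based mean that the plan already defines.

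**Conclusion.** The concern holds in its conditional form. The plan averages a person-level score over knees, permits two study knees per patient, and states no variance that allows for it. If bilateral patients are present, a simple 90% CI has a one-sided error of 5.4% to 8.7% instead of 5%, for 5% to 30% of patients bilateral and a correlation of 0.5 to 1. Those ranges are assumptions, since the documents give neither quantity. With no bilateral patients there is no error at all.

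The sample-size arithmetic is correct, and power at 140 evaluable knees is adequate throughout. The change should be made because the bias runs in the device's favour on both decision rules and because fixing the variance now removes a choice that could otherwise be made after the data are seen. Confidence is medium, because the bilateral share is unknown.

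**What to change.** In section 9.1.4, state that the 90% CI of mean 10-year KSS Function uses a patient-clustered (cluster-robust) variance with the patient as the cluster, and report the number of patients beside the number of knees. Apply the same variance to the confidence intervals for the other person-level scores, such as SF-12 and LEAS. Enrolment and the Kaplan-Meier analysis need no change.

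The cost is a short addition to the SAP and a patient identifier that links the two knees of one person; no new data are collected. The downside is a somewhat wider interval, by about 2% to 21% in the scenarios shown. If no patient has two study knees, the clustered interval is essentially the simple one.
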